#### 8.6. Safety Analysis

All safety data collected on or after the randomization date through 30 days after the date of the last dose of study drug will be summarized by treatment group (according to the study drug received). Data for the pretreatment period and after the date of last dose of study drug plus 30 days will be included in data listings.

#### 8.6.1. Extent of Exposure

A participant's extent of exposure to study drug data will be generated from the study drug administration data. Exposure data will be summarized by treatment group.

#### **8.6.2.** Adverse Events

Clinical and laboratory AEs will be coded using the current version of the Medical Dictionary for Regulatory Activities. System organ class, high-level group term, high-level term, preferred term, and lower-level term will be attached to the clinical database.

Events will be summarized on the basis of the date of onset for the event. A treatment-emergent AE will be defined as any AE that begins on or after the date of first dose of study drug up to the date of last dose of study drug plus 30 days.

Summaries (number and percentage of participants) of treatment-emergent AEs (by system organ class, and preferred term) will be provided by treatment group.

#### 8.6.3. Laboratory Evaluations

Selected laboratory test data (using conventional units) will be summarized using only observed data. Data and change from baseline at all scheduled time points will be summarized.

Graded laboratory abnormalities will be defined using the grading scheme in DAIDS Table for Grading the Severity of Adult and Pediatric Adverse Events, Version 2.1 (corrected, July 2017).

Incidence of treatment-emergent laboratory abnormalities, defined as values that increase at least 1 toxicity grade from baseline at any time postbaseline up to the date of last dose of study drug plus 30 days will be summarized by treatment group. If baseline data are missing, then any graded abnormality (ie, at least a Grade 1) will be considered treatment-emergent.

Laboratory abnormalities that occur before the first dose of study drug or after the participant has been discontinued from treatment for at least 30 days will be included in a data listing.

#### 8.7. Adjustments for Multiplicity

The overall two-sided type I error rate of 0.05 for the primary and key  $\alpha$ -controlled secondary endpoints will be controlled using the Lan-DeMets approach with O'Brien-Fleming type spending function accompanying a gatekeeping testing strategy (ie, the primary efficacy endpoint will be tested first, and the key  $\alpha$ -controlled secondary endpoints will be tested only if the primary efficacy endpoint is met). The O'Brien-Fleming approach will be used for decision making. The information fraction and the actual stopping boundaries will depend on the exact timing of the interim analysis. Example decision boundaries are shown in Table 12.

DMC Scenario Example	Interim Efficacy Boundary (One-Sided P Value)	Interim Futility Boundary (One-Sided P Value)	Final Two-Sided P Value
Second DMC occurs at 50% of primary endpoint events (0.5 information fraction)	≤ 0.0015	> 0.5055	≤ 0.0490
Second DMC occurs at 50% of enrollment (0.35 information fraction) and the third DMC at 50% of primary endpoint events (0.5 information fraction)	2nd DMC: ≤ 0.0002 3rd DMC: ≤ 0.0015	2nd DMC: > 0.8342 3rd DMC: > 0.5128	≤ 0.0490

Table 12.Boundaries for Interim and Final Analysis

DMC = data monitoring committee

#### 8.8. Pharmacokinetic Analysis

Plasma concentrations and pharmacokinetic parameters for GS-5245 metabolite, GS-441524, will be listed and summarized using descriptive statistics by treatment. Exposure-safety and efficacy may be conducted as needed, if sufficient data are available.

#### 8.9. Sample Size

A total of 2300 participants provides > 90% power to detect a ratio of 0.25 (GS-5245 to placebo) in the primary endpoint (proportion of COVID-19–related hospitalization or all-cause death by Day 29), which is equal to a hazard ratio of 0.25 using a 2-sided significance level of 0.05 assuming the placebo event rate is 2% in the placebo group. The estimate of 2% in the placebo group is based on the placebo event rate for COVID-19 in the EPIC-SR study {Pfizer Inc 2022} and vaccine efficacy data from the Centers for Disease Control and Prevention Morbidity and Mortality Weekly Report {Ferdinands 2022, Thompson 2022}.

The sample size may be increased based on the unblinded sample size re-estimation. The sample size calculation was performed using software EAST (Version 6.5, module for log-rank test given accrual duration and study duration and 1 or 2 interim analyses using the Lan-DeMets approach with O'Brien-Fleming type spending function, with sample size re-estimation).

#### 8.9.1. Sample Size Re-estimation

A sample size re-estimation is planned at the interim analysis when approximately 50% of expected primary endpoint events occur, due to the uncertainty in hospitalization or death rate in the placebo arm. All possible interim results will be partitioned into 3 zones–Favorable, Promising, and Unfavorable–depending on the size of observed conditional power (CP) under the current trend at the interim. If the CP falls into the Favorable zone, the study will continue

with the originally planned sample size of 2300 patients. If the CP falls into the Promising zone, the total sample size may be increased. If the CP falls into the Unfavorable zone but the interim result has not met the futility boundary, the study will also continue with the originally planned sample size of 2300 patients.

The DMC will review the unblinded data at the interim analysis and communicate the decision on sample size to the study team. The overall type I error is controlled at 0.05 using the method proposed by Cui-Hung-Wang approach {Cui 2019, Muller 2004}. Further details will be included in the DMC charter and an adaptation plan.

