#### Number of Participants Planned:

Approximately 2300 participants will be randomized into this study. Up to 3150 participants may be enrolled depending on the sample size re-estimation result.

**Target Population:** Nonhospitalized participants with COVID-19 with at least 1 risk factor (if unvaccinated) and at least 2 risk factors (if vaccinated at any point) for disease progression.

Duration of Intervention: Participants will receive oral GS-5245 or placebo for 5 days.

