#### **Statistical Methods:**

A total of 2300 participants provides > 90% power to detect a ratio of 0.25 (GS-5245 to placebo in the primary endpoint [proportion of COVID-19–related hospitalization or all-cause death by Day 29], which is equal to a hazard ratio of 0.25) using a 2-sided significance level of 0.05 assuming the event rate is 2% in the placebo group.

[figure not shown]
The primary endpoint will be analyzed using a Cox proportional hazards model with the stratification factors (duration of symptoms and vaccination status) as covariates. The hazard ratio and 95% CI will be provided.

A gatekeeping approach will be used for testing the key secondary endpoints. The endpoints will be tested in the following sequential order:

- Proportion of participants with all-cause hospitalization by Day 29.
- Proportion of participants with COVID-19-related MAVs or all-cause death by Day 29.
- Proportion of participants with COVID-19-related MAVs by Day 29.
- Proportion of participants with all-cause death by Day 29.

An unblinded interim analysis of efficacy and futility is planned after 50% of planned participants complete the Day 29 assessment or prematurely discontinue from the study, or 50% of expected primary endpoint events occur, whichever comes first. If the interim is triggered by 50% of enrollment, an additional unblinded interim analysis may be conducted after 50% of expected events have occurred. The unblinded interim analysis at 50% of expected events will include a sample size re-estimation.

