#### 8.2.1.1. Data Monitoring Committee Analysis

The first DMC meeting will be based on data collected after the first 200 participants have reached Day 29 or prematurely discontinued from the study and will include safety data.

The second DMC meeting will be based on data collected after 50% of planned participants complete the Day 29 assessment or prematurely discontinue from the study, or 50% of expected primary endpoint events occur, whichever happens earlier. The DMC meeting will include review of safety and formal evaluation of futility and efficacy. The DMC may provide recommendation on stopping enrollment to the study if the prespecified boundaries for efficacy (outlined in Section 8.7) or futility are crossed. If the second DMC meeting is triggered by 50% planned enrollment, a third DMC meeting may be conducted after 50% of expected primary endpoint events as appropriate. If the second DMC meeting is triggered by 50% of expected primary endpoint events, a third DMC meeting is not planned. An interim analysis communication plan will be created.

Further details are provided in the DMC charter.

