# 8.10. Data Monitoring Committee

A multidisciplinary DMC consisting of non-Gilead personnel will review the progress of the study, perform interim review of safety data after the first 200 participants have reached Day 29 or prematurely discontinued from the study, and provide recommendation to Gilead whether the nature, frequency, and severity of AEs associated with study drug warrant the early discontinuation of the study in the best interests of the participant, whether the study should continue as planned, or whether the study should continue with modifications. The DMC may also provide recommendations as needed regarding study design. The DMC will have 2 or 3 formal (unblinded data review) meetings. The first formal meeting will review safety data after the first 200 participants complete the Day 29 assessment or prematurely discontinue from the study. The second formal meeting will review safety, efficacy, and futility data after 50% of participants complete the Day 29 assessment or prematurely discontinue from the study or 50% of expected primary endpoint events have occurred, whichever happens earlier. If the second DMC meeting is triggered by 50% of planned participants completing the Day 29 visit or prematurely discontinuing, a third DMC meeting may be conducted after 50% of expected primary endpoint events, as appropriate. The DMC may make a recommendation of stopping enrollment to the study if the prespecified efficacy or futility stopping criteria are met.

The DMC's specific activities will be defined by a mutually agreed charter, which will define the DMC's membership, conduct, and meeting schedule.

While the DMC will be asked to advise Gilead regarding future conduct of the study, including possible early study discontinuation, Gilead retains final decision-making authority on all aspects of the study. If the DMC recommends stopping the study for lack of efficacy, a Gilead Oversight Committee will be unblinded to confirm the DMC recommendation.

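### Is the planned sample size re-estimation undermined because the look that carries it is optional when enrolment reaches 50% first?

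*Protocol*

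**What the plan says.** Section 8.9.1 of the protocol says of the re-estimation step that it "is planned at the interim analysis when approximately 50% of expected primary endpoint events occur, due to the uncertainty in hospitalization or death rate" among placebo recipients. The decision uses three zones, "depending on the size of observed conditional power (CP) under the current trend at the interim". The Synopsis sets the ceiling: "Up to 3150 participants may be enrolled depending on the sample size re-estimation result".

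The Synopsis (Statistical Methods) ties the step to one look only: "The unblinded interim analysis at 50% of expected events will include a sample size re-estimation". The sentence before it says that, if the enrolment count triggers the first efficacy look, "an additional unblinded interim analysis may be conducted after 50% of expected events have occurred". Section 8.2.1.1 says the same of the DMC ("a third DMC meeting may be conducted after 50% of expected primary endpoint events as appropriate"), and so does section 8.10 ("a third DMC meeting may be conducted after 50% of expected primary endpoint events, as appropriate").

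Section 8.10 allows for two or three formal DMC meetings, and section 8.9 for one or two interim analyses. Table 12 in section 8.7 gives example boundaries for two cases: the events-first order, and "Second DMC occurs at 50% of enrollment (0.35 information fraction) and the third DMC at 50% of primary endpoint events (0.5 information fraction)". Sections 8.2.1.1, 8.9.1 and 8.10 defer details to the DMC charter, and 8.9.1 also to an adaptation plan.

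**The concern.** Read alone, section 8.9.1 promises a safeguard against an uncertain placebo rate. Read with the other sections, the safeguard exists only if the look at 50% of expected events is held, and that look becomes discretionary when enrolment gets there first. A low event rate is what makes enrolment get there first.

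The protocol gives no criterion for holding the look. It does not say whether the choice may draw on unblinded results from the second DMC meeting, and Table 12 has no row for the enrolment-first order with the later look skipped. Section 8.9.1 could also be thought to give a reason that its rule does not serve, because the zones turn on conditional power and not on the event rate.

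At stake would be the chance to raise the sample size from 2300 towards 3150 in a trial short of events, and possibly type I error if the choice to hold the look were informed by treatment results.

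**Working it through.** **Inputs from the documents.** N = 2300, 1:1; placebo rate 2%; ratio 0.25, so 0.5% on GS-5245; two-sided alpha 0.05 (section 8.9). O'Brien-Fleming type spending, with example information fractions 0.35 and 0.5 (section 8.7). Accrual rate, event timing and zone limits are not given and are assumed where needed.

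**Stated power.** Expected events = 1150 × 0.02 + 1150 × 0.005 = 28.75. The Schoenfeld formula gives Φ(√28.75 × ln 4 / 2 − 1.96) = 0.96; a pooled comparison of two proportions gives 0.90. This agrees with section 8.9 (above 90%) and SAP 1.3 (about 90%).

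**Boundaries.** Lan-DeMets spending at one-sided 0.025 gives 0.0015 at fraction 0.5 and 0.00015 at 0.35, with a final two-sided level of 0.0490 for looks at 0.5 and 1 and also for looks at 0.35, 0.5 and 1. All match Table 12 after rounding. For looks at 0.35 and 1 only, the path without the third look, the same recursion gives a final level of 0.0499. The spending function therefore supplies the missing row.

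**Which trigger comes first.** Half of 28.75 is 14.4, so the event trigger is 14 or 15. The chance that enrolment comes first is the probability of fewer than 14 (or 15) events in two binomial arms. With 575 per arm, only the 1150 completers count. With 725 per arm, 300 further participants count in full (an assumption). At hazard ratio 0.25:

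| Placebo rate | Completers only | 300 more counted |
|---|---|---|
| 2% | 0.42-0.53 | 0.13-0.20 |
| 1.5% | 0.80-0.87 | 0.51-0.61 |
| 1.4% | 0.86-0.92 | 0.61-0.71 |
| 1% | 0.98-0.99 | 0.92-0.96 |

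The event trigger carries no Day 29 condition, so the right-hand column is nearer to what would happen with brisk accrual. The direction is the same in both. The 1.4% row is the rate implied by Table 12's 0.35 fraction if follow-up is complete: 0.35 × 28.75 / 1150 / 0.625 = 1.4%. The protocol evidently foresaw this order.

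**What holding the look is worth.** Simulated trials (300,000 per setting) took the enrolment-first cases that reach the event trigger before 2300. They assumed a Promising zone starting at conditional power 0.3 or 0.5 and ending at 0.8 or 0.9, an increase straight to 3150, and Table 12's third-look bounds; stopping at the second look was ignored. Power with the look held minus power with it skipped, at hazard ratio 0.25:

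| Placebo rate | Difference (percentage points) |
|---|---|
| 2% | +0.2 to +3.4 |
| 1.5% | −0.2 to +6.1 |
| 1.4% | 0.0 to +6.8 |
| 1% | −0.8 to +9.0 |

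Only 7-34% of such trials at 1.4% fall in the Promising zone, which is why the average is modest. Mean N in these trials rises from 2300 to about 2360-2590.

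**When the look cannot occur.** At a 1% placebo rate, 2300 participants yield 2300 × 0.00625 = 14.4 expected events. The chance that all 2300 give fewer than 14 or 15 is 0.43-0.53. A rule making the look compulsory would need an exception for this.

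**Type I error.** If the choice to hold or skip used second-look results and the final level were recomputed for each path, the worst case is 0.0253 one-sided against 0.025. Using 0.0490 at the final analysis on either path removes the excess.

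**Does the reason fit the rule?** Take 14 events split 11 to 3: z = 8/√14 = 2.14. Conditional power under the trend, against a final two-sided 0.0490, is 0.94 if projected to 28.75 events. Projected to about 20 events (2300 × 0.014 × 0.625 = 20.1), it is 0.86. With an upper zone limit of 0.9 the lower rate moves the trial from Favorable to Promising. Section 8.9.1 does not say which event count is used, so a mismatch is not shown.

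**The case for a change.** The best case for a change is that section 8.9.1 uses firm language for a step that three other places make conditional, and that the condition bites when the stated reason for the step applies. The remedy looks cheap: a few words, one meeting, and about 0.001 of nominal level at the end (0.0490 against 0.0499). Within the Promising zone the gain from holding the look at a 1.4% placebo rate is +5 to +25 points under the assumed limits. An unwritten choice made after unblinded results have been seen is also poor form, even when its effect on error is small.

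The difference in wording stands, and so does the direction of the event-rate effect. The rest is weaker. The Synopsis places the optional look and the re-estimation in adjacent sentences, so a reader is told that one depends on the other. The qualifier in sections 8.2.1.1 and 8.10 naturally covers a stop at the second meeting or a trigger never reached. Section 8.10 assigns the meeting schedule to the charter and final decisions to the sponsor. Neither the charter nor the adaptation plan is public, so their silence cannot be assumed. Table 12 is labelled as examples, and section 8.7 says the actual boundaries depend on timing.

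**Conclusion.** No change to the plan is needed. Re-estimation that depends on whether a second efficacy look is held is a legitimate design choice, and the protocol discloses it. Both paths lead to a valid test, with at most 0.0003 one-sided excess error in the worst case and none if 0.0490 is kept throughout.

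Making the look compulsory would be a trade-off. At placebo rates of 1% to 2% and a hazard ratio of 0.25, the average power effect runs from −0.8 to +9.0 points, in return for an extra futility bound and more participants. Those figures rest on assumed zone limits and a direct increase to 3150. The trigger-order ranges (13-53% at a 2% placebo rate, 51-87% at 1.5%) rest on how many participants in follow-up are counted; at the lowest rates the look may never be reached.

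For this trial the point is moot. SAP 2.1.1, 2.3 and 6.5 record that enrolment stopped with fewer than half the participants randomized, because of a low event rate, and that no interim efficacy or futility analysis was done. The optional wording did not cause that and does not touch the final analysis.

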# 8.10. Data Monitoring Committee

A multidisciplinary DMC consisting of non-Gilead personnel will review the progress of the study, perform interim review of safety data after the first 200 participants have reached Day 29 or prematurely discontinued from the study, and provide recommendation to Gilead whether the nature, frequency, and severity of AEs associated with study drug warrant the early discontinuation of the study in the best interests of the participant, whether the study should continue as planned, or whether the study should continue with modifications. The DMC may also provide recommendations as needed regarding study design. The DMC will have 2 or 3 formal (unblinded data review) meetings. The first formal meeting will review safety data after the first 200 participants complete the Day 29 assessment or prematurely discontinue from the study. The second formal meeting will review safety, efficacy, and futility data after 50% of participants complete the Day 29 assessment or prematurely discontinue from the study or 50% of expected primary endpoint events have occurred, whichever happens earlier. If the second DMC meeting is triggered by 50% of planned participants completing the Day 29 visit or prematurely discontinuing, a third DMC meeting may be conducted after 50% of expected primary endpoint events, as appropriate. The DMC may make a recommendation of stopping enrollment to the study if the prespecified efficacy or futility stopping criteria are met.

The DMC's specific activities will be defined by a mutually agreed charter, which will define the DMC's membership, conduct, and meeting schedule.

While the DMC will be asked to advise Gilead regarding future conduct of the study, including possible early study discontinuation, Gilead retains final decision-making authority on all aspects of the study. If the DMC recommends stopping the study for lack of efficacy, a Gilead Oversight Committee will be unblinded to confirm the DMC recommendation.

# 9. **RESPONSIBILITIES**

#### 9.1. Investigator Responsibilities

#### 9.1.1. Good Clinical Practice

The investigator will ensure that this study is conducted in accordance with ICH E6(R2) addendum to its guideline for GCP and applicable laws and regulations.

#### 9.1.2. Financial Disclosure

The investigator and subinvestigators will provide prompt and accurate documentation of their financial interest or arrangements with the sponsor or proprietary interests in the study drug. This documentation must be provided before the investigator's (and any subinvestigator's) participation in the study. The investigator and subinvestigator agree to notify Gilead of any change in reportable interests during the study and for 1 year following completion of the study. Study completion is defined as the date when the last participant completes the protocol-defined activities.

# 9.1.3. Institutional Review Board/Independent Ethics Committee Review and Approval

The investigator (or Gilead as appropriate according to local regulations) will submit this protocol, ICF, and any accompanying material to be provided to the participant (such as advertisements, participant information sheets, or descriptions of the study used to obtain informed consent) to an IRB/IEC. The investigator will not begin any study participant activities until approval from the IRB/IEC has been documented and provided as a letter to the investigator.

Before implementation, the investigator will submit to and receive documented approval from the IRB/IEC for any modifications made to the protocol or any accompanying material to be provided to the participant after initial IRB/IEC approval, with the exception of those necessary to reduce immediate risk to study participants.

#### 9.1.4. Informed Consent

The investigator is responsible for obtaining written informed consent from each individual participating in this study after adequate explanation of the aims, methods, objectives, and potential hazards of the study before undertaking any study-related procedures. The investigator must use the most current IRB/IEC approved ICF for documenting written informed consent. Each ICF will be appropriately signed and dated by the participant or the participant's legally authorized representative, the person conducting the consent discussion, and an impartial witness (if required by IRB/IEC or local requirements).

The ICF will inform participants about planned sample retention. In addition to the study-specific ICF to be signed by each participant participating in the study, participants will be required to document additional consent to provide additional samples in accordance with applicable regulations. The results of the tests performed on the samples will not be given to the participant or the investigator. The stored biological samples will be destroyed no later than 15 years after the end of study or per country requirements, but participants may at any time request that their stored samples be destroyed.

